## 5.2 TRISMUS

Cryotherapy did not significantly affect maximum mouth opening during the postoperative period ( $F_{(1,16)} = 0.006$ ,  $p = 0.93$ ). However, a significant effect of time ( $F_{(2,32)} = 45.410$ ,  $p < 0.001$ ) and a significant interaction between treatment and time ( $F_{(2,32)} = 4.703$ ,  $p = 0.016$ ) were observed.

Mouth opening decreased on postoperative day 2 compared with baseline in both the control group ( $43.8 \pm 8.9$  vs.  $30.1 \pm 12.2$ ;  $p < 0.001$ ) and the cryotherapy group ( $39.3 \pm 8.8$  vs.  $31.4 \pm 7.9$ ;  $p < 0.01$ ). In Group A, mouth opening remained significantly reduced on postoperative day 7 compared with baseline ( $43.8 \pm 8.9$  vs.  $37.8 \pm 13.6$ ;  $p = 0.005$ ). In contrast, Group B showed recovery of mouth opening by day 7, with values comparable to baseline ( $39.3 \pm 8.8$  vs.  $40.5 \pm 8.5$ ;  $p = 0.43$ ) (Table 2).

[figure not shown]

Table 2: Average of maximal mouth opening values on days 0, 2 and 7 post-op.

Correlation analysis revealed no significant association between pain intensity

and trismus in Group B on postoperative days 2 ( $r = 0.15$ ,  $p = 0.54$ ) or 7 ( $r = 0.11$ ,  $p = 0.66$ ). In contrast, a significant positive correlation was observed in Group A on postoperative day 7 ( $r = 0.62$ ,  $p = 0.005$ ), indicating that greater pain intensity was associated with increased mouth opening restriction. No correlation was found on postoperative day 2 in Group A ( $r = 0.30$ ,  $p = 0.23$ ) (Table 3).

[figure not shown]

Table 3: Correlation between pain and trismus for control group.

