#### **4.4 SAMPLE**

The sample selection consisted on patients referred to the Federal University of Rio Grande do Sul's Dentistry School. The selected patients require bilateral extraction of lower third molars under local anesthesia in two different surgical times. There will be no change to the routine care for patients volunteering in the study. The surgical procedures will be performed by the research team responsible for this study. Participants of both sexes, aged 18 to 50 years, were included in the study if they presented an indication for bilateral surgical removal of mandibular third molars in similar positions according to Pell and Gregory classification. Additional inclusion criteria comprised the absence of systemic comorbidities, local conditions free of inflammatory or infectious processes, no history of allergy to the prescribed medications, and no recent or chronic use of antibiotics, anti-inflammatory drugs, corticosteroids, or analgesics. Participants were excluded from the study if they used medications other than those prescribed by the surgeon, failed to provide the required data, belonged to Group A (control) but used postoperative ice packs, or belonged to Group B (test) and did not use ice packs as instructed by the researchers. There were three dropouts due to noncompliance with postoperative recommendations and the use of non-prescribed medication, resulting in 34 procedures performed in 17 patients.

Postoperative consultations were conducted for follow-up, suture removal, and the evaluation and treatment of any potential postoperative complications.

The selection of the control group and experimental groups were determined by a simple randomization in the immediate postoperative period. One surgical site didn't receive cryotherapy (GA), while the other site received cryotherapy with ice (GB).

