#### 4.8 STATISTICAL ANALYSIS

Data normality was assessed using the Kolmogorov–Smirnov test. Parametric analyses were applied to compare groups (control side vs. test side) and postoperative time points (from day 0 to day 7). Continuous variables, including pain intensity (VAS scores), maximum mouth opening (mm), and facial edema (mm), were expressed as means  $\pm$  standard deviation (SD).

A two-way repeated-measures analysis of variance (ANOVA), followed by Fisher's least significant difference (LSD) post hoc test, was used to evaluate the main effects of time and treatment, as well as their interaction, for pain intensity, trismus, and edema. Pain reports were also qualitatively analyzed based on the frequency distribution of pain categories (no pain, mild pain, moderate pain, and severe pain) for both groups.

Associations between pain intensity and trismus or edema were assessed using Pearson's correlation coefficient. Trismus and edema were additionally evaluated using the formulas (Baseline – Postoperative) and (Postoperative – Baseline), respectively. Qualitative data related to quality of life were presented as percentages.

All statistical analyses were performed using SPSS software (version 20.0; IBM Corp., Armonk, NY, USA). Statistical significance was set at  $P < 0.05$ .

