### 5.3 EDEMA

Time significantly affected postoperative edema ( $F_{(2,32)} = 10.34$ ,  $p < 0.001$ ), whereas treatment ( $F_{(1,16)} = 0.516$ ,  $p = 0.48$ ) and the interaction between factors ( $F_{(2,32)} = 1.533$ ,  $p = 0.23$ ) did not.

Both groups exhibited greater edema on postoperative day 2 compared with baseline (Group A:  $123.0 \pm 5.1$  vs.  $126.2 \pm 7.8$ ,  $p = 0.02$ ; Group B:  $123.1 \pm 7.1$  vs.  $126.3 \pm 7.5$ ,  $p = 0.005$ ). No significant differences were observed between baseline and postoperative day 7 in either Group A ( $123.0 \pm 5.1$  vs.  $126.1 \pm 7.8$ ;  $p = 0.86$ ) or Group B ( $123.1 \pm 7.1$  vs.  $123.5 \pm 8.7$ ;  $p = 0.71$ ), indicating resolution of edema by the end of the evaluation period in both groups (Table 4).

[figure not shown]

Table 4: Average of edema values on days 0, 2 and 7 post-op.

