A strong association was also observed between higher pain intensity reports and increased requests for rescue medication in the control group. These results indicate that failure to use cryotherapy may increase reliance on pharmacological interventions to manage postoperative discomfort, which could otherwise be mitigated through a simple and low-cost intervention such as ice pack application for 30 minutes over a 12-hour period. Therefore, the proposed cryotherapy protocol can be considered a safe and effective approach that enhances postoperative predictability, facilitates complication control, and promotes greater patient engagement in self-care.

Trismus represents a multifactorial postoperative response influenced by surgical trauma, including osteotomy, extracellular fluid extravasation, tissue hemorrhage, and muscle fiber incision. Given the simultaneous occurrence of these factors, significant benefits of cryotherapy are not expected before consolidation of the inflammatory response, which explains the absence of intergroup differences during the first 72 postoperative hours. However, when comparing immediate postoperative measurements with those obtained on postoperative day 7, the control

group exhibited significantly greater mouth opening limitation (Table 2), indicating a longer duration of trismus. This finding is supported by the statistically significant correlation between pain intensity and trismus observed exclusively in the control group (Table 3), suggesting that higher pain levels are associated with prolonged mouth opening restriction. These results were further corroborated by the quality-of-life questionnaire, which revealed greater difficulty in mouth opening among control participants.

Edema did not show statistically significant differences between groups (Table 4), consistent with previous reports. It is hypothesized that superficial ice application may be insufficient to significantly reduce edema due to its limited penetration into deeper muscular and facial tissue planes, thereby restricting its vasoconstrictive effects.

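### The treatment test for mouth opening and edema averages in day 0, so the mouth-opening p = 0.93 is not a statement about the postoperative period

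*Combined protocol and SAP*

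**What the plan says.** Section 4.8 specifies a two-way repeated-measures ANOVA that "was used to evaluate the main effects of time and treatment, as well as their interaction, for pain intensity, trismus, and edema", over "postoperative time points (from day 0 to day 7"). The model has no baseline covariate. Change from baseline is defined for trismus and edema, but only as an additional evaluation, and no treatment test on it is reported.

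Section 5.2 states that "Cryotherapy did not significantly affect maximum mouth opening during the postoperative period" (F(1,16) = 0.006, p = 0.93). It then reports a time effect, F(2,32) = 45.410, and a treatment-by-time interaction, F(2,32) = 4.703, p = 0.016, followed by comparisons with baseline within each group. Section 5.3 has the same structure: "Time significantly affected postoperative edema" (F(2,32) = 10.34), with treatment F(1,16) = 0.516, p = 0.48.

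The Discussion gives a biological account of trismus, "which explains the absence of intergroup differences during the first 72 postoperative hours", and also says that limitation on day 7 was significantly greater in the control group.

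The descriptions of the day-0 mouth-opening value do not agree. Section 4.5 has one measurement before the first surgery, used for both procedures. Section 4.7 lists it among postoperative days 0, 2 and 7. Section 5.2 calls it baseline and prints a different mean for each side. The Discussion calls it immediate postoperative.

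**The concern.** A main effect of treatment in this model is the side difference averaged over all time levels. If one level is a baseline, the average is not a postoperative effect: a baseline gap in the opposite direction cancels it, and a zero gap dilutes it by one third. A reader of section 5.2 would take p = 0.93 as strong evidence of no effect on mouth opening after surgery, which is not what was tested.

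The text supplies no replacement. For pain, section 5.1 compares the two sides on days 1 and 3. For mouth opening, section 5.2 gives no side difference, interval or p value for day 2 or day 7. The Discussion nevertheless asserts no difference in the first 72 hours and a significant difference on day 7. Neither statement rests on a between-side estimate given in the text.

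**Working it through.** **Inputs.** n = 17 patients, each contributing both sides (section 4.4: "resulting in 34 procedures performed in 17 patients"). Mouth-opening means from section 5.2, mm, at days 0, 2, 7: A (control) 43.8, 30.1, 37.8; B (cryotherapy) 39.3, 31.4, 40.5. Edema means from section 5.3: A 123.0, 126.2, 126.1; B 123.1, 126.3, 123.5. F values as quoted above. All differences d are B minus A.

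**1. Reproduce the reported results.** F(1,16) = 0.006 gives p = 0.939 (printed 0.93, apparently truncated). F(2,32) = 4.703 gives p = 0.016, as printed. Two numerator degrees of freedom for time mean three time levels, so day 0 is in the model.

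**2. What the main effect estimates.** d = (-4.5, +1.3, +2.7). Mean = -0.5/3 = -0.17 mm. The 4.5 mm day-0 gap almost exactly offsets the 4.0 mm sum of the follow-up differences. The implied SE is 0.167/√0.006 = 2.15 mm.

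**3. Error variance implied by the printed F values.**
- Interaction: SS = (17/2) × Σ(d - mean)² = 247.7; MS = 247.7/2 = 123.9; error MS = 123.9/4.703 = 26.3.
- Time: the means over both sides are 41.55, 30.75 and 39.15. MS = 34 × 64.32/2 = 1093.4; error MS = 1093.4/45.410 = 24.1.

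These are different error terms, so agreement is not proof. It does fit an analysis of raw values with day 0 as a level.

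**4. Days 2 and 7 only, raw values.** Estimate (1.3 + 2.7)/2 = +2.0 mm. Assuming compound symmetry of the paired differences, the between-patient component is 17 × 2.15² - 2 × 26.3/3 = 61.1. SE = √((61.1 + 26.3)/17) = 2.27; t = 0.88 on 16 df; p about 0.39; 95% CI 2.0 ± 2.12 × 2.27, about -2.8 to 6.8. Rounding of the printed means and F moves p over 0.12 to 0.57. Using the printed SDs with assumed A-B correlations of 0 to 0.9 gives 0.17 to 0.58.

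**5. Change from day 0** (error MS 26.3, 32 df).

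| Contrast | Estimate, mm | SE | 95% CI | p |
|---|---|---|---|---|
| Day 2 | 1.3 + 4.5 = +5.8 | √(4 × 26.3/17) = 2.49 | 0.7 to 10.9 | 0.03 |
| Day 7 | 2.7 + 4.5 = +7.2 | 2.49 | 2.1 to 12.3 | 0.007 |
| Average | 2.0 + 4.5 = +6.5 | √(3 × 26.3/17) = 2.16 | 2.1 to 10.9 | 0.005 |

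On 16 df the average has CI 1.9 to 11.1 and p = 0.008. A covariate-adjusted estimate is 2.0 + 4.5 × slope, so it lies between +2.0 and +6.5 mm for any slope from 0 to 1.

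**6. Does the interaction escape the problem?** Set the day-0 gap to zero, as one shared baseline would require, and hold the error MS: d = (0, 1.3, 2.7), Σ(d - mean)² = 3.647, MS = 8.5 × 3.647/2 = 15.5, F = 15.5/26.3 = 0.59, p about 0.56. The reported interaction therefore depends on the same gap.

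**7. Edema.** d = (+0.1, +0.1, -2.6). The three-level average is -0.80 mm (p = 0.48); days 2 and 7 alone give -1.25 mm (p about 0.32); change from baseline gives -1.35 mm (p about 0.39). Nothing cancels, and no version is significant. These figures are provisional. In Group A, 126.2 against 123.0 is given p = 0.02 on day 2, but 126.1 against 123.0 is given p = 0.86 on day 7. The implied error MS also differs: 13.5 from the interaction, 8.4 from time.

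**The case against.** The strongest reply is that section 5.2 does not stop at the main effect. Its next sentence reports a significant interaction, the term that tests whether change over time differs between sides, and reading the interaction is an accepted approach and part of the stated plan. The trial's conclusion favours cryotherapy on mouth opening, so the null main effect does not drive it. This stands as far as it goes. But the interaction is a two-degree-of-freedom test with no direction, size or interval, and step 6 shows that it rests on the day-0 gap.

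A reader might infer a false null: that cryotherapy improved mouth opening by 6.5 mm and the analysis hid it. The documents do not support this. Without day 0 the difference is +2.0 mm and not significant, so the day-0 gap explains why p is 0.93 rather than about 0.4, not why the result is non-significant. The +6.5 mm credits the whole 4.5 mm gap to treatment, and the source of that gap is unknown. One shared baseline in 17 patients cannot give both 43.8 and 39.3. If a value was taken before each surgery, the Discussion says that 11 patients had the control side first, so most Group B baselines would follow an earlier extraction, and residual limitation or an order effect could produce the gap. If it was taken after surgery, it is not a preoperative value at all, and section 4.6 starts ice immediately after surgery.

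It is also fair that the intervals are back-calculated. The Group A SD rises from 8.9 to 12.2 and 13.6, which strains a common error variance. A model chosen now is post hoc.

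**Conclusion.** The mouth-opening sentence in section 5.2 is wrong as written. F(1,16) = 0.006 tests an average over days 0, 2 and 7 (-0.17 mm), not the postoperative period, and its near-zero size arises from a day-0 gap of -4.5 mm against follow-up differences of +1.3 and +2.7 mm.

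Whether there is a postoperative effect cannot be settled from the documents. The estimate runs from +2.0 mm (p about 0.39) to +6.5 mm (95% CI about 2.1 to 10.9) according to how day 0 is handled. The 72-hour explanation has the same weakness: the day-2 difference is +1.3 mm raw and +5.8 mm as change from day 0.

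Edema is not an equal case. The construction is the same, but the effect is dilution only, and the finding of no significant treatment effect is unchanged.

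The -0.17 and +2.0 mm estimates need only the printed means. The standard errors, intervals and recomputed p values in steps 4 to 7 also need the back-derived error variance, held common across days, and, for the days 2 and 7 contrast, compound symmetry. Patient-level data would replace these assumptions.

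**What to change.** 1. Reconcile sections 4.5, 4.7, 5.2 and the Discussion on when the day-0 mouth-opening value was taken, whether there is one per patient or one per surgery, and why the sides differ by 4.5 mm.
2. In section 4.8, model mouth opening on days 2 and 7 only, with treatment, day, treatment by day, and patient. Add the day-0 value as a covariate if it was measured before each surgery. If it is one shared value, it cancels within patient and the model holds without it. Report the side difference with 95% CI overall and by day, labelled post hoc.
3. In section 5.2, describe F(1,16) = 0.006 as an average over days 0, 2 and 7, or remove it. In the Discussion, replace the 72-hour explanation with the day-2 estimate and its interval.
4. Apply the same model to edema for consistency, after resolving the conflict between the Group A day-7 mean and its p value.

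Cost: re-analysis of data already collected, one degree of freedom for the covariate, some rewording, and a post hoc label on the new estimates.

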### 2.2 SPECIFIC OBJECTIVES

- Measure the interincisal distance (in millimeters) on postoperative days 0, 2, and 7.
- Evaluate trismus by measuring the maximum interincisal opening with the patient seated and the tragus–ala plane parallel to the ground, using the average of three consecutive mouth openings.
- Compare the levels of postoperative discomfort associated with anesthetic agents using a visual analog scale (VAS).

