#### **4.5 SURGICAL TECHNIQUE**

All surgical procedures were performed by a team composed of two trained and calibrated surgeons, exclusively during the morning period. Each patient was treated by the same surgeon for both surgical procedures. A standardized surgical protocol was applied in all cases and included anamnesis, clinical examination, and collection of vital signs (blood pressure and heart rate).

Patients were positioned in the dental chair and underwent antisepsis of the oral cavity and adjacent extraoral region using 0.12% aqueous chlorhexidine. After establishment of a sterile surgical field, local anesthesia was administered via inferior

alveolar, lingual, and buccal nerve blocks using 2% mepivacaine with 1:100,000 epinephrine. A mucoperiosteal incision was made extending from the retromolar area to the mesial aspect of the second molar, with a relaxing incision in an open L-shaped design to expose the underlying bone. Under copious saline irrigation, osteotomy was performed in the distobuccal region using a #6 round bur, and odontosection was carried out when necessary using a 702 surgical bur. Following tooth removal, wound closure was achieved with simple interrupted sutures using 4-0 silk sutures.

Prior to the first surgical procedure, maximum mouth opening was measured in millimeters using a measuring tape to determine the interincisal distance. In cases where maxillary or mandibular incisors were absent, the occlusal edges were used as reference points. This measurement was used as a baseline parameter for comparison between procedures.

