#### **4.6 POSTOPERATIVE CARE**

In the immediate postoperative period following the first surgical procedure, the allocation of postoperative care—with or without cryotherapy—was randomized using a simple draw. Allocation was determined by the selection of a folded paper indicating Group A or Group B and was supervised by a third party to ensure allocation concealment. When the first surgical site of a patient was assigned to Group A (control), the contralateral site in the second surgical procedure was assigned to Group B (test), and vice versa.

Group A (control) did not receive postoperative cryotherapy. Group B (test) was instructed to apply standardized ice packs (11 × 8.5 × 1 cm), provided by the research team, positioned diagonally to cover both the mandibular angle and the cheek on the operated side. Cryotherapy was initiated immediately after surgery under surgeon supervision and continued for the first 12 postoperative hours, consisting of 30-minute applications followed by 30-minute intervals (total of 12 applications). During the intervals, patients were instructed to store the ice packs in a freezer until the next application.

All participants received identical pharmacological postoperative instructions (APPENDIX B) for both interventions, including paracetamol 1 g every 6 hours for 3 days and mouth rinses with 0.12% aqueous chlorhexidine digluconate twice daily for 7 days, starting on the day following surgery. In cases of persistent pain, trismus, or edema that significantly interfered with daily activities despite the use of prescribed analgesics, patients were instructed to use rescue medication consisting of codeine 30 mg every 4 hours as needed.

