## 4.7 STUDY VARIABLES

The outcome variables of this study were postoperative pain, trismus, local edema, and changes in quality of life following mandibular third molar extraction. Postoperative assessments were performed by the research team, consisting of two calibrated surgeons and one supervising professor, on postoperative days 0 (day of surgery), 2, and 7. The following evaluation protocols were applied:

a) Pain assessment: postoperative pain was assessed using a visual analog scale (VAS– APPENDIX C) ranging from 0 to 10, in which 0 represented no pain, 1–3 mild pain, 3.1–6 moderate pain, and 6.1–10 severe pain. Patients completed the scale at home daily until postoperative day 7.

b) Trismus assessment: trismus was evaluated by measuring maximum mouth opening with the patient seated and the tragus–ala plane parallel to the ground. Patients were instructed to open their mouths three consecutive times, and the mean value was recorded. Measurements were obtained as the interincisal distance in millimeters using a measuring tape. In the absence of maxillary or mandibular incisors, the occlusal edges were used as reference points. Measurements were recorded on postoperative days 0, 2, and 7.

c) Edema assessment: facial edema was measured using the method described by Gabka and Matsumura. Three linear facial measurements were obtained in millimeters with a measuring tape: tragus to pogonion, tragus to oral commissure, and lateral canthus to mandibular angle. The mean of these three measurements was calculated to quantify edema. This assessment was performed preoperatively and on postoperative days 2 and 7.

d) Quality of life assessment: quality of life was evaluated using a questionnaire adapted from the OHIP-14 (APPENDIX D), consisting of 14 dichotomous (yes/no) questions addressing daily functional limitations. The questionnaire included items related to chewing and swallowing ability, dietary changes, alterations in taste, mouth opening, voice changes, speech intelligibility, facial appearance, sleep disturbances, and ability to perform work-related activities. The questionnaire was provided to participants on the day of surgery and completed on postoperative days 0, 2, and 7. At the conclusion of the evaluation period following the second intervention, participants also answered the question: “Which intervention did you perceive as resulting in greater postoperative improvement?”

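### The mouth-opening baseline is defined in conflicting ways, and the claim that cryotherapy shortens trismus depends on which definition was used

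*Combined protocol and SAP*

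**What the plan says.** **Baseline.** Section 4.5: "Prior to the first surgical procedure, maximum mouth opening was measured in millimeters using a measuring tape to determine the interincisal distance", and then "This measurement was used as a baseline parameter for comparison between procedures". Section 2.2 sets the objective "Measure the interincisal distance (in millimeters) on postoperative days 0, 2, and 7", and section 4.7 repeats for trismus: "Measurements were recorded on postoperative days 0, 2, and 7". For edema, section 4.7 uses different words: "This assessment was performed preoperatively and on postoperative days 2 and 7". Section 6 describes the day-7 comparator for mouth opening as the measurement made straight after the operation. Appendix D labels the first questionnaire column as pre-op, although section 4.7 calls that time point day 0. Section 4.6 adds: "Cryotherapy was initiated immediately after surgery under surgeon supervision".

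**Results.** Section 5.2 gives (mean ± SD, mm):

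| | Day 0 / baseline | Day 2 | Day 7 |
|---|---|---|---|
| Group A (control) | 43.8 ± 8.9 | 30.1 ± 12.2 | 37.8 ± 13.6 |
| Group B (ice) | 39.3 ± 8.8 | 31.4 ± 7.9 | 40.5 ± 8.5 |

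The treatment main effect is F(1,16) = 0.006, p = 0.93. The treatment-by-time interaction is F(2,32) = 4.703, p = 0.016. Against its own baseline at day 7, Group A has p = 0.005. For Group B the text reads "In contrast, Group B showed recovery of mouth opening by day 7, with values comparable to baseline", with p = 0.43.

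**Questionnaire.** Section 5.4 reports difficulty opening the mouth at day 7 in 31% (A) and 23.5% (B) and counts this among three significant items. Section 4.8 names no test for it: "Qualitative data related to quality of life were presented as percentages".

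**Claims.** The abstract, section 6 and section 7 present less or shorter trismus as an effect of cryotherapy.

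**The concern.** All 17 patients contribute to both sides (section 4.4; degrees of freedom 16 and 32). A single baseline per patient would therefore give identical means and SDs in the two groups. The printed values differ by 4.5 mm, so either the baseline was not the one section 4.5 describes, or a figure is wrong.

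Three accounts of day 0 are possible from the text: once before the first surgery, before each surgery, or after each surgery. They have different consequences. A postoperative value is not a preoperative reference, and because ice starts immediately after surgery it may already carry treatment.

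The form of the argument adds to the problem. A significant change on one side and a non-significant change on the other is not a test of the difference between sides. In the printed text the interaction is the only significant between-side test of measured mouth opening, and it too rests on the day-0 values.

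At stake is one of the headline benefits. A reader cannot tell whether the data show a between-side effect on trismus or an artefact of the reference value.

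**Working it through.** **Inputs.** The means, SDs and F values in section 5.2; n = 17 from section 4.4. Tests are taken as two-sided. Correlations are not reported, so they are assumed and shown as ranges.

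**1. Reproduce the printed interaction.** F = 4.703 on (2, 32) df gives p = 0.016, as printed. Differences B − A: day 0 −4.5, day 2 +1.3, day 7 +2.7 mm; mean −0.167.
- Interaction SS = (17/2) × Σ(D − mean D)² = 247.7; MS = 247.7/2 = 123.9.
- Implied error MS = 123.9/4.703 = 26.3.

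**2. Share of the day-0 gap.** Difference in change at day 7 = 2.7 − (−4.5) = 7.2 mm; the gap is 4.5/7.2 = 62.5% of it. At day 2 the difference in change is 1.3 + 4.5 = 5.8 mm.

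**3. Reading 1: one shared baseline.** The day-0 difference is zero by construction, so D = (0, 1.3, 2.7).
- Interaction SS = 31.0; MS = 15.5. With the error held, F = 15.5/26.3 = 0.59, p = 0.56.
- With the error rebuilt from the printed SDs, Var(d) = sA² + sB² − 2·r·sA·sB at days 2 and 7, where r is the between-side correlation and ρ the correlation between the day-2 and day-7 differences:

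| r | ρ | interaction p |
|---|---|---|
| 0 | 0 | 0.82 |
| 0.5 | 0.5 | 0.62 |
| 0.9 | 0.9 | 0.16 |
| 0.99 | 0.9 | 0.045 |

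- The day-7 difference is 2.7 mm whatever the shared value, because it cancels. Paired t, 16 df:

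| r | p | 95% CI (mm) |
|---|---|---|
| 0 | 0.50 | −5.5 to 10.9 |
| 0.5 | 0.36 | −3.4 to 8.8 |
| 0.8 | 0.21 | −1.7 to 7.1 |
| 0.9 | 0.13 | −0.9 to 6.3 |

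**4. Reading 2: valid preoperative value at each surgery.** SE of the difference in change = √(4 × 26.3/17) = 2.49 mm, 32 df.
- Day 7: 7.2 mm, 95% CI 2.1 to 12.3, p = 0.007.
- Day 2: 5.8 mm, 95% CI 0.7 to 10.9, p = 0.026.

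**5. Is the day-0 gap chance?** Paired t for 4.5 mm: p = 0.16, 0.052 and 0.004 at r = 0, 0.5 and 0.8. The printed figures do not settle it.

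**6. Questionnaire item.** With at most 17 patients, 23.5% fits only 4/17, and 31% fits only 5/16 or 4/13. Over all possible pairings the smallest exact McNemar p is 0.50 (5/16) or 0.125 (4/13). A paired test of this item at day 7 could not have reached 0.05.

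**The case against.** The strongest reply is that the single baseline is not what was analysed. Two printed means with different SDs, and trismus results given for days 0, 2 and 7, fit a day-0 value taken at each surgery. Section 4.5 does not say that opening was measured only once. Section 4.8 separates baseline from postoperative values in its trismus formula, and Appendix D's pre-op label supports a preoperative day 0, so the section 6 description may be a slip. On that reading the planned interaction test is a genuine between-side result and the difference in change supports the claim. Table 2 is not shown and might carry a between-side comparison. The questionnaire is also a different measure from interincisal distance.

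Much of this stands. Reading 2 may well be the true one, and the figures under Reading 1 rest on assumed correlations. The 62.5% share is not in itself evidence of error. But section 4.5 states that the measurement made before the first surgery served for comparing the procedures, and nothing in the text withdraws that. Inferring from the results which baseline was used does not replace stating it. Even under Reading 2, neither the difference in change nor its interval appears in the text, and the claim is argued from the within-side p-values. The questionnaire matters here only because section 6 cites it as corroboration.

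**Conclusion.** The concern holds and must be fixed. No single account of day 0 satisfies sections 2.2, 4.5, 4.7, 5.2 and 6 together, and the trismus conclusion turns on which applies. With one shared baseline, the day-7 difference of 2.7 mm is small and imprecise, and the interaction is unlikely to be significant: among the values tried it fell below 0.05 only with assumed correlations of 0.99 and 0.9 together. With valid separate preoperative values, the interaction and the 7.2 mm difference in change stand. If day 0 was measured after surgery, neither analysis has a proper baseline.

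Confidence is high for the contradiction and for the dependence on it. It does not extend to whether cryotherapy affects mouth opening, which needs the patient-level data. Separately, the abstract's statement that Group B was free of trismus at the end of follow-up sits awkwardly beside 23.5% of that group reporting difficulty opening at day 7.

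**What to change.** 1. State when day-0 opening was measured (once before the first surgery, before each surgery, or after surgery) and make sections 2.2, 4.5, 4.7, 5.2 and 6 agree. If there is one pre-first-surgery value, use it for both sides and rerun the ANOVA.
2. Replace the contrast of within-side tests with the paired between-side difference at days 2 and 7, with 95% CIs, from patient-level data. Adjust for the preoperative value at each surgery if it exists. If the only day-0 value was taken after surgery, do not use it as the baseline.
3. Report the interaction together with the day-0 difference.
4. Print the counts and the paired test for the mouth-opening questionnaire item, or stop calling it significant.
5. Align the trismus statements in the abstract, discussion and conclusion with these results. If a single baseline applies and the paired difference is not significant, say that a between-side difference was not demonstrated and that the estimate is imprecise. If separate preoperative values are confirmed, base the claim on the difference in change and its CI.

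**Cost.** Re-analysis of data already collected and rewording; no new data. Adjusting for a preoperative value at each surgery uses one degree of freedom with 17 pairs. The trismus claim may become less favourable.
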